### **11.1 PRO Assessments**

In both conditions, PRO survey data will be collected directly from patients during the following assessment periods:

- T1: Pre-intervention (time period: Within 30 days prior to start of 1st intervention session);
- T2: After the 5th intervention session (time period: Within 21 days after the 5th session);
- T3: After the 10th intervention session (Time period: Within 21 days after the 10th session); and
- T4: At post-intervention after the 14th session (Time period: within 14 days after the 14th session).

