### **12.3 Patient-Reported Outcome Measures (Aim #4)**

To address specific aim #4, several PRO measures will be collected to evaluate primary, secondary and exploratory outcomes to examine the temporal associations and strength of associations among variables in the preliminary conceptual described in Figure 1. PROs will be collected from all participants at four PRO time points (T1-T4). Collection of PRO data serves several preparatory functions for the efficacy trial including making final selection of PROs, contributing to sample size calculations, and exploring preliminary relationships with other variables in the causal pathway.

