## **14 PRIMARY PATIENT-REPORTED OUTCOME MEASURES**

Several of the NIH Patient-Reported Outcomes Measurement System (PROMIS®) short forms will be used to measure primary outcomes such as health status, mental health symptoms, and physical health symptoms. We have found the PROMIS® surveys to have good psychometrics in HCV patients. *The primary patient-reported outcomes will be the mean T-scores at T1 (Baseline) and T4 (end of intervention):*

- 14.1** PROMIS Global Health Status Mental Health Mean T-Score
- 14.2** PROMIS Global Health Status Physical Health Mean T-Score
- 14.3** PROMIS Depression Mean T-score
- 14.4** PROMIS Anger Mean T-score
- 14.5** PROMIS Anxiety Mean T-score
- 14.6** PROMIS Fatigue Mean T-score
- 14.7** PROMIS Sleep Disturbance Mean T-score
- 14.8** PROMIS Pain Interference Mean T-score

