## **23 DATA ANALYSIS**

### **23.1 Statistical Analysis Overview**

The analysis strategies are designed to inform the feasibility and planning of a subsequent efficacy RCT. No hypothesis tests will be conducted. Statistical estimates will be reported with 95% confidence intervals (CIs) or standard deviations. Collectively, the results of this preparatory study will allow us to formulate reasonable expectations for the subsequent RCT. A publicly available PROMIS® scoring system is available for computing PROMIS T-scores. Statistical computations will be performed in SAS software (SAS Institute, Cary, NC).

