### **23.5 Aim 4: Explore changes in patient outcomes, mediators and intervention targets, as well as temporal associations and strength of associations among variables in a preliminary conceptual model, to inform a future efficacy trial**

For each outcome measured before, during and after the intervention, we will obtain estimates of specific mean changes, treatment effects, standard deviations, serial correlations, corresponding confidence intervals indicating levels of precision or standardized effect size estimates (Cohen's *d*) of change. We anticipate that mean changes will favor the VC-CBCS intervention relative to SC.

Various exploratory methods may be used to fully examine the data and generate hypotheses to be evaluated in a future RCT. We may explore the weekly repeated measures for intervention targets and potential mediators/intermediate outcomes to identify targets rated as strongest by patients, and to identify the timing and magnitude of changes in mediators/intermediate outcomes during the VC-CBCS. To better understand potential causal pathways and refine the conceptual model, we may explore temporal correlations among targets, mediators (intermediate/secondary outcomes) and primary patient-reported and clinical outcomes. For example, we may explore associations of mediators with intervention-induced changes in health status, physical and mental symptoms, salivary cortisol, ALT and AST. We will estimate mean  $\log_{10}$  cortisol as a diurnal function of time of day and compute summary values such as the area under the curve (AUC), AUC minus ground, and cortisol awakening.

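### Aim 4 points to an arm difference in change for the eight primary PROs without using the T1 score as a covariate, and T1 may be self-reported after participants learn their arm

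*Combined protocol and SAP*

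**What the plan says.** **Estimand and reporting.** Section 14 defines the eight primary PROs by arm-level summaries: "The primary patient-reported outcomes will be the mean T-scores at T1 (Baseline) and T4 (end of intervention". It states no contrast between arms. Section 23.5 goes further. For each outcome, "we will obtain estimates of specific mean changes, treatment effects, standard deviations, serial correlations" are to be produced, together with "corresponding confidence intervals indicating levels of precision or standardized effect size estimates" (Cohen's d) of change, and the stated expectation is that "We anticipate that mean changes will favor the VC-CBCS intervention relative to SC". The general rule in Section 23.1 is "Statistical estimates will be reported with 95% confidence intervals (CIs) or standard deviations". That section also rules out hypothesis tests.

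**Availability of T1 and use of the results.** Section 12.3 states that "PROs will be collected from all participants at four PRO time points (T1-T4", and lists "contributing to sample size calculations" for the efficacy trial among the purposes of these data.

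**Timing.** Section 11.1 ties T1 to the first session only: "Within 30 days prior to start of" session 1. Section 8 randomises a wave once it is full, after which participants are telephoned with their assignment. Sections 10.2 and 10.3 put the workbook mailing and the technology training before session 1. Section 5 requires consent before data collection and before randomisation, but does not order those two against each other. Table 2 marks PROs and randomisation in the same column 0.

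**The concern.** Two gaps affect the same estimates.

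First, the natural reading of Section 23.5 is a difference between arms in mean change. A change score fixes the coefficient on T1 at 1. When T1 and T4 are imperfectly correlated this subtracts too much, and it leaves part of any chance baseline imbalance in the estimate. A model with T1 as covariate estimates that coefficient and is more precise, using data the study already has.

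Second, VC-CBCS participants need to know their arm before session 1 to receive training and materials. The later part of the 30-day window can therefore fall after the notification call. A symptom score self-reported after the arm is known is no longer a clean pre-allocation baseline, and the change, adjusted and T4-only estimates can then differ for reasons unrelated to the intervention.

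The stake is the quality of the effect sizes and variances passed on to the efficacy trial.

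**Working it through.** The plan gives no precision figure for Aim 4, so there is none to reproduce.

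**Inputs from the protocol.** 24 VC-CBCS and 8 SC (Section 3.1); VC-CBCS groups of 5, 7, 6 and 6 (Section 8); retention expected above 80% (Section 23.2).

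**Assumptions, not in the documents.** Equal SD at T1 and T4 and in both arms; T1–T4 correlation r from 0.3 to 0.8. Results are in SD units.

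**Formulas.** k = 1/24 + 1/8 = 0.1667 and N = 32.
- Change score: SE = √[2k(1 − r)], half-width with t(30).
- T1-adjusted: SE = √[k(1 − r²)(1 + 1/(N − 4))], half-width with t(29). The last factor, 1 + 1/28, is the price of estimating the slope.

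| r | SE change | SE adjusted | SE reduction | Half-width change | Half-width adjusted |
|---|---|---|---|---|---|
| 0.3 | 0.483 | 0.396 | 18% | 0.99 | 0.81 |
| 0.4 | 0.447 | 0.381 | 15% | 0.91 | 0.78 |
| 0.5 | 0.408 | 0.360 | 12% | 0.83 | 0.74 |
| 0.6 | 0.365 | 0.332 | 9% | 0.75 | 0.68 |
| 0.7 | 0.316 | 0.297 | 6% | 0.65 | 0.61 |
| 0.8 | 0.258 | 0.249 | 3% | 0.53 | 0.51 |

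**Attrition.** With 20 versus 7 at T4 (83% and 88%, assumed), the adjusted half-width is 0.88–0.56 SD over the same r.

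**Clustering.** The table ignores the four VC-CBCS groups. In simulation with an assumed intraclass correlation of 0.05 or 0.10 at T4, the adjusted SE rises by about 3–8% or 7–17%. Half-widths become about 0.84–0.55 or 0.86–0.59 SD. These still use t(29), so with only four groups they are lower bounds. The gain over change scores stays at about 17% to 3%.

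**Timing.** Let knowledge of the arm shift VC-CBCS reports by s1 at T1 and s4 at T4. The bias is s4 − s1 for change, s4 − r·s1 for adjusted, and s4 for T4 means. With an assumed shift of 0.1 to 0.5 SD:

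| Shift present at | Change | Adjusted, r = 0.5 | Adjusted, r = 0.8 | T4 means |
|---|---|---|---|---|
| T1 only (bias reversed in sign) | 0.1–0.5 | 0.05–0.25 | 0.08–0.40 | 0 |
| T1 and T4 alike | 0 | 0.05–0.25 | 0.02–0.10 | 0.1–0.5 |
| T4 only (T1 before the call) | 0.1–0.5 | 0.1–0.5 | 0.1–0.5 | 0.1–0.5 |

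No estimator is safe in every row. Putting T1 before the call makes the three agree, but leaves the T4 shift in all of them.

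**Would dropping late T1 surveys help?** Suppose a quarter are late in each arm, leaving 18 versus 6. The adjusted half-width is then 0.96, 0.92, 0.87, 0.80, 0.72 and 0.60 SD at r = 0.3 to 0.8. The plain change score on all 32 gives 0.99, 0.91, 0.83, 0.75, 0.65 and 0.53. From r = 0.4 upward, exclusion costs more precision than adjustment gains.

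**Cohen's d.** Scaled by the change SD rather than the baseline SD, d is multiplied by 1/√[2(1 − r)]: 0.85, 1.00, 1.29 and 1.58 at r = 0.3, 0.5, 0.7 and 0.8.

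**The case against.** The strongest reply is that Aim 4 is exploratory. There are no tests, Section 14 states no contrast between arms, and the 3:1 split was chosen to study feasibility and the VC-CBCS arm closely. At r = 0.8 adjustment moves the half-width only from 0.53 to 0.51 SD. If the same reporting shift occurs at T1 and T4, the change score is unbiased and the adjusted estimate is not. All of this is fair. It limits the weight of the point and argues for showing the estimates together where T1 timing is in doubt. It does not remove the case for adjusting, because treatment effects relative to SC are promised and the data are meant to inform a sample size.

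Three stronger readings are tempting, and the documents do not support them.
- *That treatment effects will appear without confidence intervals.* The two uses of 'or' are loose, but Section 23.5 does list corresponding intervals among its outputs. This is wording to tighten.
- *That Cohen's d will be uninterpretable.* SDs and serial correlations are planned outputs, so a reader can rescale d. Only the label is missing.
- *That baselines were in fact taken after notification.* Section 11.1 equally allows every T1 survey to precede the call. The plan permits late baselines; it does not schedule them.

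Practicality is also a fair objection. Section 22 describes a REDCap audit trail that can date surveys, but nothing says the date of the telephone call is recorded, so a retrospective check may not be possible. Some outcome descriptions in Section 15 are already in the past tense, so a scheduling rule may come too late for some or all waves.

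**Conclusion.** The point holds as a modest improvement to the estimation plan. Section 23.5 implies a difference in change relative to SC and leaves out a covariate already collected from all participants. Using it lowers the SE by about 18% to 3% for r from 0.3 to 0.8 at 24 versus 8, and the interval remains at least ±0.5 SD. The size depends on the assumed r and on equal SDs, and allowing for clustering or attrition widens the intervals further.

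The timing gap is real in the text: no section places T1 before arm notification. Its effect is unknown, since both the occurrence of late surveys and the shift of 0.1 to 0.5 SD are hypothetical. A reader might infer that the Aim 4 results are invalid, or that late T1 surveys should be discarded. Neither follows. No test is planned whose validity could fail, and exclusions made after notification are not protected by randomisation and can widen the intervals.

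**What to change.** 1. **Name the estimator in Section 23.5.** For each primary PRO, define the treatment effect as the VC-CBCS minus SC difference in T4 T-score from a linear model with arm and T1 T-score, reported with its 95% CI. One named repeated-measures model over T1–T4 is equally acceptable, and also uses T2 and T3 from people missing T4. State that the CI does not allow for the four VC-CBCS groups, unless the model does so. Keep T1 and T4 means and mean changes as descriptive output.
2. **For any wave not yet started,** collect T1 PROs after the wave is full and before the notification call, using the email or telephone routes in Section 22 where iPad training has not yet taken place. This removes only the T1 part of any reporting shift; T4 self-report stays unblinded.
3. **For waves already run,** if notification dates were kept, report by arm how many T1 surveys followed the call, and show the adjusted, change and T4-mean estimates side by side. Do not exclude late T1 surveys, and do not present any of the three as unbiased. If the dates were not kept, say so.
4. **Minor wording:** name the SD that scales Cohen's d.

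The cost is a few sentences, one standard SAS model, one degree of freedom (already counted above) and some scheduling care at T1. No participants, visits or measures are added.

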## **24 STUDY CONDUCT**

This study will be conducted in accordance with federal and institutional guidelines

(<https://www.hhs.gov/ohrp/regulations-and-policy/regulations/finalized-revisions-common-rule/index.html>;

<https://www.hhs.gov/ohrp/regulations-and-policy/regulations/finalized-revisions-common-rule/index.html>)

and relevant Good Clinical Practice (GCP) Guidelines described by the International Conference on Harmonization (ICH). The study will be conducted in compliance with this version of the study protocol. The protocol and any amendments will receive UNC Institutional Review Board (IRB) approval prior to initiation of the study. Study personnel involved in conducting this study will be qualified by education, training, and experience to perform their respective tasks.

We will apply all standard protections of patient confidentiality and data integrity during this study. Consent forms will be uploaded to REDCap and hard copies stored in a secure, locked location. All research data will be stored on a secure electronic server, behind a firewall at UNC, maintained and monitored by the UNC SOM ITS. Study documents will be stored in locked and secure file cabinets and on the CGIBD secure server in a folder accessible only to study staff. Audio-video files of the intervention will be uploaded to the CGIBD secure server to the private research folder.

## **25 DATABASE RETENTION**

The REDCap database and all study-related materials will be maintained until all data are published and up to 5-7 years after the end of the study at UNC by the PI in collaboration with the NC TraCS Institute and SOM ITS. Hard copy data will be securely stored on the secure server and in locked cabinets. Access to electronic folders and REDCap will be terminated for staff no longer working on the project. Data initially stored on screened patients who were not enrolled will be deleted at the end of the study. If datasets are exported for analysis, no identifiers or contact information will be exported.

## 26 DATA AND SAFETY AND MONITORING PLAN

This study has a full DSMP that has been reviewed and approved by the NIH National Institute of Nursing Research (NINR) and is in accordance with the Policy of the NINR for Data and Safety Monitoring of Extramural Clinical Trials. Available in supplementary attachment. Study staff will adhere the guidelines in the DSMP.

### 26.1 Procedures for Adverse Events (from DSMPv2.0 - 27Sept2019)

In brief, we will identify, review, and report study-related serious adverse events (SAEs) according to UNC regulatory guidelines and OHRP Guidance on Reviewing and Reporting Unanticipated Problems Involving Risks to Subjects or Others and Adverse Events. The UNC IRB Standard Operating Procedures (dated: 6/2/2017) defines a reportable serious adverse events (SAE) as any event temporally associated with the subject's participation in research that meets any of the following criteria: 1) results in death, 2) is life threatening, 3) requires inpatient hospitalization or prolongation of existing hospitalization, 4) results in persistent or significant disability/incapacity, 5) results in congenital anomaly/birth defect, or 6) any other adverse event that, based on appropriate medical judgement, may jeopardize the subject's health and may require medical or surgical intervention to prevent one of the outcomes listed above (UNC SOP 1401: 3.2.2.1.1). These SAEs will be reported immediately to the PI and [name], the Independent Safety Monitor (ISM), within 48 hours of notification. The PI and ISM will review the SAE and determine if the SAE is partially or fully related to study participation. (Note: We do not anticipate any study-related SAEs or AEs based on prior experience conducting these interventions and as this is a minimal risk behavioral intervention including no drugs, devices or procedures). Based on SAE review and ISM, the SAE outcome/conclusion will be recorded with study records. If the SAE is determined to be study-related, an ISM summary will be reported to the UNC IRB within 7 calendar days. If not study-related, it will be tracked but not reported. Unanticipated study-related AEs or problems will be reported within 14 days to the IRB. We will record SAEs and unanticipated study-related AEs in a regulatory binder. The NINR Program Officer will be notified of study-related SAEs or study-related unanticipated AEs within one month of reporting the event to the UNC IRB (per OHRP Guidance recommendations).

The target population has a higher prevalence of medical, psychiatric, and substance use disorders and conditions. Therefore, we anticipate learning about non-study related patient issues related to liver, cirrhosis, psychiatric, or substance use issues due to the natural history of these disorders and higher risk of these disorders in the target population. Under this protocol, the PI and ISM will not report non-study related events such as inpatient hospitalizations for medical conditions or symptoms (e.g., complaints of fatigue, nausea, pain) to the IRB or sponsor, although reports of these events will be tracked in a regulatory binder. We will follow a SOP to handle non-study related medical or psychiatric issues.

[name] will provide oversight and direct patient care commensurate with good clinical practice as a clinical psychologist and member of the UNC Liver Program. We do not anticipate any events that would halt accrual. If an event should occur, it would be discussed with ISM, staff and telemental health consultants. A review of eligibility criteria, patient monitoring, assessments, or the intervention may occur but is unlikely to halt accrual.

## 28 GLOSSARY OF TERMS

A1C – Hemoglobin A1C

AE- adverse event

ALT - alanine aminotransferase

AST - aspartate aminotransferase

BRFSS - Behavioral Risk Factor Surveillance System

CB – cognitive behavioral

CBCS - cognitive behavioral coping skills

CBSM – cognitive behavioral stress management

CBT – cognitive behavioral treatment

CGIBD- Center for Gastrointestinal Biology and Diseases

CTSA – clinical and translational science awards

CONSORT – Consolidated Standards for Reporting of Trials

DSMP – data safety monitoring plan

HCV- hepatitis C virus

HCV-PEG – Hepatitis C Virus Patient Engagement Group

HCV RNA – HCV RNA PCR test

IMB - informational-motivation-behavioral skills

IRB – Internal Review Board

MOCS - Measure of Current Status-Part A

NC TraCS- North Carolina Translational & Clinical Sciences Institute

NIH- National Institutes of Health

NINR – National Institute of Nursing Research

PRO- patient-reported outcomes

PROMIS- Patient Reported Outcomes Measurement System

PROP UP – patient reported outcomes project of HCV-TARGET

PSS – perceived stress scale

HRQOL- health-related quality of life

RCT - randomized controlled trial

REDCap - research electronic data capture system

SAE – serious adverse event

SAMISS - Substance Abuse and Mental Illness Brief Symptom Screener

SC – standard of care

SM – stress management

VC - videoconference

